### 5.1 DEFINITIONS OF DOSE-LIMITING TOXICITIES

**Incidence of Dose Limiting Toxicities (DLT).** Time frame: 28 days (1 cycle of therapy followed by laboratory evaluation for toxicity on Cycle 2 Day 1, Study Day 29) Toxicity will be assessed using the National Cancer Institute (NCI) Common Toxicity Criteria for Adverse Events (CTCAE), version 4.03

[http://ctep.cancer.gov/protocolDevelopment/electronic\\_applications/ctc.htm](http://ctep.cancer.gov/protocolDevelopment/electronic_applications/ctc.htm) unless otherwise specified. A DLT is defined as an adverse event or abnormal laboratory value assessed as at least possibly related to the study medication, that occurs  $\leq$  29 days or prior to the Cycle 2, Day 1 visit (whichever is longer) following the first dose, and meets any of the protocol-specified DLT criteria.

**Dose-limiting toxicity:** The dose-limiting toxicity described in this section refers to toxicity derived from any or all of the agents used in the combination regimen.

#### Hematologic:

- Grade 3 neutropenia (ANC <1,000/mm^3) that does not resolve to  $\leq$  Grade 2 within 3 weeks with the use of growth factor

- Grade 4 neutropenia (ANC <500/mm^3)
- Febrile neutropenia (ANC <1,000/mm^3 with a fever  $\geq 38.3^{\circ}\text{C}$ )
- Grade 4 thrombocytopenia (<25,000/mm^3) that persists for  $\geq 7$  days, despite holding treatment
- Grade 3 thrombocytopenia associated with Grade  $\geq 2$  bleeding or requiring RBC or platelet Transfusions

Non-Hematologic:

- Any Grade 3 or higher non-hematologic adverse event where relationship to study drug(s) cannot be ruled out (Note: excludes rituximab infusion reactions)
- Grade  $\geq 3$  nausea, vomiting, or diarrhea uncontrolled by maximal supportive care and persisting greater than 7 days
- Grade 3 fatigue persisting for greater than 7 days
- Treatment delay of any drug greater than 7 days for toxicity

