## 5. TREATMENT

The investigator will instruct the patient to take the study drugs as per protocol. All dosages prescribed and dispensed to the patient and any dose change or interruption must be recorded in the dosage administration record CRF, as appropriately.

This is an open-label dose escalation study using a 3+3 design. Before applying the dose escalation rules, 3 subjects in any given cohort must have completed the DLT observation period which is defined as 28 days (1 cycle) of therapy followed by evaluation for toxicity on Cycle 2 Day 1 (Study Day 29 +/- 3 days). The dose level in which 2 patients experience unacceptable toxicity is usually considered the maximum administered dose (MAD). We will define the MTD as the next lower dose level in which no more than 1/6 patients experience unacceptable toxicity. Dose escalation will cease if 2 or more patients develop DLT. There will be no intrapatient dose escalation.

Enrollment in a cohort will proceed as follows:

- If no dose limiting toxicity (DLT) is observed during the DLT observation period in the initial 3 subjects of a cohort, dose escalation to the next higher dose level cohort will occur.
- If 1 DLT is observed, 3 additional subjects will be enrolled at the same dose level for a total of at least 6 subjects. If no further DLT(s) are observed, escalation to the next higher dose level cohort will occur.

Dose escalation will occur at the planned dose levels until the MTD is determined or until the highest dose level is tested. The MTD is defined as the highest dose at which <33% of the subjects enrolled in a cohort experience a DLT. At least 6 subjects will be treated at the MTD or highest tested dose.

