**Table 1 Dose Modifications for Hematologic Toxicity Venetoclax Monotherapy**

Hematologic Toxicity	
Event(s)	Dose Delay or Modification
Grade 3 or 4 neutropenia, without infection or fever, and/or Grade 3 or 4 thrombocytopenia, first episode	

• Hold venetoclax.

• When counts recover to <math>\leq</math> Grade 2, resume previous doses of venetoclax.

• Administer G-CSF or growth factors for neutropenia as indicated.

• If the patient was not previously receiving prophylactic G-CSF, initiate prophylactic G-CSF for neutropenia as indicated.

Grade 3 or 4 neutropenia with infection and/or fever, first episode	

• Begin anti-viral medication and hold venetoclax until fever and/or infection resolves.

• Administer G-CSF or growth factors for neutropenia as indicated.

• When counts recover to <math>\leq</math> Grade 2 and infection has been fully treated, resume previous doses of venetoclax.

• If the patient was not previously receiving prophylactic G-CSF, initiate prophylactic G-CSF for neutropenia as indicated.

Recurrent Grade 3 or 4 neutropenia with/without fever and infection despite G-CSF	

• Hold venetoclax for at least 7 days.

• Administer G-CSF or growth factors for neutropenia as indicated.

• When counts recover to <math>\leq</math> Grade 2 and/or platelets are <math>\geq 75 \times 10^9/L</math>, resume venetoclax at one dose level reduction (see Table 3).

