Grade 4 thrombocytopenia and/or symptomatic bleeding	

• Hold venetoclax for Grade 4 thrombocytopenia (platelets <math>< 25,000/\mu L</math>) or presence of symptomatic bleeding until resolution of bleeding.

• Platelets may be transfused at the discretion of the investigator.

• When platelet level rises to <math>\leq</math> Grade 2 without transfusional support for 5 consecutive days, restart venetoclax.

• For a second episode of severe thrombocytopenia and/or symptomatic bleeding, hold venetoclax. When platelet level rises to <math>\leq</math> Grade 2 without transfusional support for 5 consecutive days, restart venetoclax at one dose level reduction (see Table 3).

• For subsequent episodes of severe thrombocytopenia, hold venetoclax. When platelet level rises to <math>\leq</math> Grade 2 without transfusional support for 5 consecutive days, restart venetoclax at one dose level reduction.

G-CSF = granulocyte colony-stimulating factor.

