## **8. CONCOMITANT MEDICATIONS/PROCEDURES**

### **8.1 CONCOMITANT MEDICATIONS**

#### **8.1.1 Permitted Concomitant Medications**

Supportive medications in accordance with standard practice (such as for emesis, diarrhea, etc.) are permitted. Erythropoietic growth factors (eg, erythropoietin) and hematopoietic growth factors are allowed per institutional policy and in accordance with the ASCO guidelines (Smith 2006).

Transfusional support (packed red blood cells and platelets) may be given in accordance with institutional policy. If platelet transfusion is required during the DLT period, this will meet criteria of a DLT.

Short courses ( $\leq 14$  days) of steroid treatment for non-cancer-related medical reasons (eg, joint inflammation, asthma exacerbation, rash, antiemetic use and infusion reactions) at doses that do not exceed 100mg per day of prednisone or equivalent are permitted.

Prophylaxis for hepatitis is permitted as per local guidelines provided no contraindicated antiviral medications are used.

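### The platelet DLT rule is stricter for Grade 3 than for brief Grade 4 thrombocytopenia with Grade 2 bleeding or red-cell transfusion (narrow gap, minor wording fix)

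*Combined protocol and SAP*

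**What the plan says.** Section 5.1 and the DLT Definitions in Section 12 carry the same two platelet bullets.

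- **Grade 4** (below 25,000/mm³) is a DLT when it persists for at least 7 "days, despite holding treatment". Neither bleeding nor transfusion triggers it sooner.
- **Grade 3** is covered by a bullet that begins "Grade 3 thrombocytopenia associated with Grade" and continues with bleeding of Grade 2 or worse, or a need for red-cell or platelet transfusion. It has no duration condition.

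Other rules bear on the same patients:

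- Section 8.1.1: "If platelet transfusion is required during the DLT period, this will meet criteria of a DLT".
- Section 5.1, first non-hematologic bullet: any Grade 3 or higher non-hematologic event whose relation to study drug cannot be ruled out.
- Section 5.1, last bullet: "Treatment delay of any drug greater than 7 days for toxicity".
- Section 7.1.4, Table 1, row for Grade 4 thrombocytopenia and/or symptomatic bleeding: once platelets are at Grade 2 or better "without transfusional support for 5 consecutive days, restart venetoclax".
- Section 7.2.4.1: ibrutinib is interrupted for Grade 4 hematologic toxicity until Grade 1 or baseline.

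The count feeds the escalation rule in Section 5: "The MTD is defined as the highest dose at which <33% of the subjects enrolled in a cohort experience a DLT". The same section also describes the MTD as a level with no more than 1/6 patients affected.

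**The concern.** A toxicity rule should not become more lenient as the event becomes more severe. Here a patient at 30,000/mm³ with Grade 2 bleeding is a DLT under the platelet bullets. A patient at 20,000/mm³ for three days with the same bleeding is not. The list writes Grade ≥3 or Grade 3 or higher where it means that grade and above, so Grade 3 in this bullet cannot safely be read as Grade 3 or worse.

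DLT incidence is the primary endpoint, and single patients decide escalation: 1/6 (16.7%) passes, while 2/6 (33.3%) fails both statements of the MTD rule. The regimen also pairs platelet toxicity with bleeding risk. Section 1.3.5.5 reports ibrutinib bleeding of any grade in 44% (including bruising and petechiae) and Grade 3 or higher in 3%; Section 8.1.2.4 says up to 6% for the latter. Most bleeding is therefore below the grade that the general non-hematologic bullet catches, although the Grade 2 share is not given.

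**Working it through.** The plan states no figure for this event, so there is none to reproduce.

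**Step 1: classify the cases.** Durations under 7 days are shown as 3 days.

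| Case | Platelet bullets | Other rule (apart from delay) |
|---|---|---|
| Grade 3, 3 days, Grade 2 bleeding | DLT | – |
| Grade 3, 3 days, red-cell transfusion | DLT | – |
| Grade 4, 3 days, Grade 2 bleeding | not a DLT | none |
| Grade 4, 3 days, red-cell transfusion | not a DLT | none |
| Grade 4, 3 days, platelet transfusion | not a DLT | DLT (8.1.1) |
| Grade 4, 3 days, related Grade 3 bleeding | not a DLT | DLT (non-hematologic bullet) |
| Grade 4, 7 days | DLT | – |

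The third and fourth cases are the inversion.

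**Step 2: see how far the delay bullet closes it.** Under the Grade 4 row of Table 1, the shortest venetoclax hold is the days at Grade 4 plus 5.

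- Grade 4 for 1 or 2 days: 6 or 7 days, which is not more than 7.
- Grade 4 for 3, 4, 5 or 6 days: 8, 9, 10 or 11 days, which is more than 7 and so a DLT if a mid-cycle hold counts as a delay. The protocol does not define the term.

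The ibrutinib hold must also end within 7 days for the patient to go uncounted. Recovery to Grade 1 or baseline makes that harder. However, Section 4.1 admits patients with marrow involvement at 50,000/mm³, and for them baseline can be that low.

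Table 1 also has a row that covers neutropenia "and/or Grade 3 or 4 thrombocytopenia, first episode", which lets venetoclax resume at Grade 2 or better with no 5-day wait. A Grade 4 case with red-cell transfusion and no bleeding fits both rows. The dedicated Grade 4 row is the more natural one to apply, so I do not rely on the other.

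**Step 3: size, by illustration.** Let q be the probability that a patient falls in the gap and b the probability of any other DLT. Both are assumptions. With the gap closed, the DLT probability is p = 1 − (1 − b)(1 − q).

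The probability of passing one 3+3 level is f(p) = (1 − p)³ + 3p(1 − p)⁵. Where six patients are required (the MTD or highest tested dose), it is g(p) = (1 − p)⁶ + 6p(1 − p)⁵.

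For b = 0.10, f(b) = 0.906 and g(b) = 0.886.

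| q | p | f(p) | f(b) − f(p) | g(p) | g(b) − g(p) |
|---|---|---|---|---|---|
| 0.005 | 0.1045 | 0.899 | 0.7 points | 0.877 | 0.9 points |
| 0.01 | 0.109 | 0.891 | 1.5 points | 0.868 | 1.8 points |
| 0.02 | 0.118 | 0.875 | 3.1 points | 0.849 | 3.7 points |

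Over the same q, the 3+3 change is 0.5 to 2.2 points if b = 0.05 and 0.9 to 3.5 points if b = 0.20. The chance of at least one gap patient among six, 1 − (1 − q)⁶, is 3.0%, 5.9% or 11.4%.

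**Ceiling.** q cannot exceed the rate of Grade 4 thrombocytopenia in the DLT period, which is not given. The nearest figures combine grades and are not limited to the first cycle: Grade 3 or 4 in 8% on single-agent ibrutinib (Section 1.3.5.7), and Grade 3 and above in 20.7% on venetoclax with bendamustine and rituximab (Section 1.2.4, Study M12-630). The second includes a chemotherapy that this trial does not use.

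**The case against.** The strongest reply is that the rest of the protocol already catches nearly all of these patients. Section 5.1 counts an event that meets any of the specified criteria, the platelet-transfusion rule in Section 8.1.1 is written as a DLT rule, and Grade 4 forces holds of two drugs that often exceed 7 days. This largely stands and is why the point is minor. It does not close the gap: no rule names Grade 2 bleeding or red-cell transfusion with Grade 4, and a 1 or 2 day nadir can recover inside the delay limit. It is also fair that every q above is assumed.

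A reader might infer more than the documents support:

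- **That severe platelet toxicity with bleeding generally escapes the DLT count.** It does not; the cases in Step 1 and the hold rules show how little is left.
- **That holds starting late in Cycle 1 are a loophole of this rule**, since toxicity is judged at "evaluation for toxicity on Cycle 2 Day 1 (Study Day 29 +/- 3 days". Any truncation there affects every duration-based bullet alike. Section 5.1 sets the window as the longer of 29 days and the Cycle 2 Day 1 visit, so an early visit cannot shorten it. The three-week neutropenia criterion implies some follow-up past that visit.
- **That the lists are defective for not repeating the Section 8.1.1 rule.** That is a drafting preference; the rule already applies.
- **That the separate gastrointestinal and fatigue bullets change the count.** Where any one criterion suffices, a related Grade 3 or higher event is already a DLT. Whether short, controlled events should be exempt is a clinical choice for the sponsor.

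**Conclusion.** The inversion is real in both lists and is wrong as written, but the residual gap is narrow. It consists of brief Grade 4 thrombocytopenia with Grade 2 bleeding or red-cell transfusion and quick recovery: chiefly Grade 4 lasting 1 or 2 days, or patients with marrow involvement whose ibrutinib restart baseline can be as low as 50,000/mm³.

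Its frequency is unknown. With assumed gap rates of 0.5% to 2% and 10% other DLTs, the decision at one level changes in about 0.7% to 3.1% of trials, or 0.9% to 3.7% where six patients are required. The error always runs towards undercounting DLTs and so towards passing a dose. These figures assume independent patients and that gap events occur independently of other DLTs. Severity is minor.

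**What to change.** In the second platelet bullet of both lists (Section 5.1 and the DLT Definitions in Section 12), write: Grade ≥3 thrombocytopenia associated with Grade ≥2 bleeding or requiring RBC or platelet transfusions. Leave the Grade 4 duration bullet as it is; it still covers Grade 4 of 7 days or more without bleeding or transfusion.

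The cost is one grade symbol changed in two places. No extra data or patients are needed, and the sample size and the expansion-cohort stopping boundaries are unaffected. If the sponsor already reads Grade 3 as Grade 3 or worse, the change only records that reading.

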##### **Preliminary Safety Summary (Arm B)**

Most subjects (97.2%) in Study M12-175, Arm B experienced at least 1 treatment-emergent adverse event. An overview of adverse events, grade  $\geq 3$  adverse events, and serious adverse events reported in Study M12-175 Arm B in (please refer to Table 30 (Section 8.3.2.1.4) of the Investigator's Brochure.

The most common adverse events in Arm B (NHL subjects) were nausea (48.1%), diarrhea (44.3%), fatigue (40.6%), and vomiting and decreased appetite (20.8% each). Adverse events grade 3 and above were reported for 54.7% subjects. The most common

events grade 3 or above were anemia (16.0%) and neutropenia (12.3%). Serious adverse events were reported in 34.0% subjects. The most common serious adverse events were malignant neoplasm progression (8.5%) and diarrhea, influenza, and hyponatremia (2.8% each).

A total of 17 (16.0%) subjects experienced adverse events that led to discontinuation of venetoclax. The most common adverse events leading to discontinuation was malignant neoplasm progress (6 [5.7%] subjects) and nausea (2 [1.9%] subjects). All other events leading to discontinuation were reported in 1 subject each. A total of 9 (8.5%) subjects experienced adverse events that led to death, including 8 events of malignant neoplasm progression and 1 event of respiratory failure. All fatal events were considered to have no reasonable possibility of being related to venetoclax.

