### **1.3.5.2 Combination Therapy Studies**

The safety of ibrutinib administered as combination therapy to 130 subjects was evaluated in 3 clinical studies. In Study PCYC-1108-CA, ibrutinib is administered in combination with either the FCR (fludarabine, cyclophosphamide, and rituximab) or the BR (bendamustine and rituximab) regimen chemotherapy. In Study PCYC-1109-CA, ibrutinib is administered in combination with the monoclonal antibody ofatumumab in patients with relapsed and refractory CLL. In Study PCI-32765DBL1002, ibrutinib is administered in combination with standard R-CHOP (rituximab with cyclophosphamide, doxorubicin, vincristine, and prednisone). Across these combination studies, the most common adverse event has been diarrhea (47.7%), nausea (33.1%), infusion related reaction (29.2%), and fatigue (26.2%). Neutropenia (24.6%) has been the most common hematologic toxicity, followed by anemia (20.0%) and thrombocytopenia (19.2%).

Adverse events that were Grades 3 or 4 or higher in severity were reported in 57.7% of subjects. The most common have been hematologic: neutropenia (21.5%), anemia and thrombocytopenia (7.7% each), and febrile neutropenia (6.2%). Pneumonia (7.7%) was the most frequently reported non-hematologic Grade 3 or higher adverse event.

Overall, 36.2% of treated subjects have experienced at least 1 serious adverse event. The only event reported as related occurring in more than 2 subjects has been pneumonia. The most commonly reported serious adverse events were febrile neutropenia and pneumonia (6.2% each), cellulitis (3.8%), atrial fibrillation (3.1%), and dehydration and dyspnea (2.3% each).

Results from an ongoing Phase 1 study designed to determine the maximum tolerated dose, dose limiting toxicity, and preliminary efficacy of BR in combination with ibrutinib in 20 patients with relapsed/refractory NHL are available. Patients with at least 1 prior therapy or previously untreated but not candidates for autologous SCT were eligible. Bendamustine 90 mg/m^2 on Days 1 and 2 with rituximab 375 mg/m^2 on Day 1 were administered with escalating doses of ibrutinib (280 mg

or 560 mg) on Days 1 to 28 every 28 days for 6 cycles. Responding patients could continue ibrutinib alone after Cycle 6 until disease progression or unacceptable toxicity.

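### Neither DLT list counts a treatment-related life-threatening or fatal anemia in its own right; such an event reaches the MTD decision only indirectly, through a treatment delay of more than 7 days

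*Combined protocol and SAP*

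**What the plan says.** Section 5.1 makes an event a DLT only if it is at least possibly related, falls in the observation window and "meets any of the protocol-specified DLT criteria". The hematologic items are unresolved Grade 3 neutropenia, Grade 4 neutropenia, febrile neutropenia, persistent Grade 4 thrombocytopenia, and "Grade 3 thrombocytopenia associated with Grade" 2 or higher bleeding or with a need for red-cell or platelet transfusion. The non-hematologic items open with a general one: "Any Grade 3 or higher non-hematologic adverse event where relationship to study drug(s) cannot be ruled out". They end with "Treatment delay of any drug greater than 7 days for toxicity". Section 12 (DLT Definitions) repeats both lists.

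Three other places bear on the point:

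- Section 7.2.4.1 interrupts ibrutinib for Grade 4 hematologic toxicity until recovery to Grade 1 or baseline.
- Section 8.1.1 permits red-cell and platelet transfusion under institutional policy. It makes a required platelet transfusion in the DLT period a DLT and is silent on red cells.
- Table 1 (Section 7.1.4), on venetoclax hematologic toxicity, has no anemia row.

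**The concern.** The primary objective (Section 2.1) is the MTD or recommended phase II dose, judged by DLT incidence, and venetoclax is the drug being escalated. Section 1.2.3 names decreased erythrocytes among its primary nonclinical toxicities and describes the falls in hematocrit and hemoglobin as dose-related. Section 7.3 reports roughly doubled venetoclax exposure with the ibrutinib dose used here (six mantle cell patients). The program summary in Section 1.2.4 names neutropenia, anemia and thrombocytopenia as the leading Grade 3+ events. The DLT lists cover two of these three.

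A dose level could thus be cleared although a patient had a drug-related anemia that was life-threatening or fatal. With cohorts of three to six and a limit of one DLT in six, a single uncounted event can change the decision.

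**Working it through.** **1. Does any criterion catch a related life-threatening anemia?**

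| Route | Catches it? |
|---|---|
| Hematologic items (5.1, 12) | No. None names anemia or hemoglobin. |
| Red-cell transfusion | Only as a qualifier of Grade 3 thrombocytopenia. |
| Grade 3+ general item | No. It is limited to non-hematologic events. |
| Platelet-transfusion rule (8.1.1) | No. There is no red-cell counterpart. |
| Delay of more than 7 days | Partly. The ibrutinib hold in 7.2.4.1 can trigger it. A case that recovers to Grade 1 or baseline within 7 days escapes, and the heading leaves open whether hematologic toxicity is meant. |
| Unacceptable toxicity in the MTD rule (5, 12) | No separate definition, so it adds nothing. |

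**2. How frequent is Grade 3+ anemia in the cited studies?**

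- M12-175 Arm B (monotherapy, 106 patients): anemia 16.0% = 17/106, neutropenia 12.3% = 13/106. Anemia leads by four patients.
- M12-630 (with bendamustine and rituximab, 58 patients): neutropenia 48.3% = 28/58, lymphocyte decrease 34.5% = 20/58, thrombocytopenia 20.7% = 12/58. Anemia is not among the three listed.
- The program summary names neutropenia first.

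**3. How frequent is the event at issue?** Section 13.1.2 classes every life-threatening or fatal event as serious, so serious anemia includes all the cases of interest. The NHL safety summary in Section 1.2.4 reports no serious anemia in monotherapy (131 treated) and none in more than one subject in combination trials (215 treated).

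- Upper value: the one-sided 95% bound from 0/131 is 1 − 0.05^(1/131) = 2.3%.
- Lower value: 1/215 = 0.47%, rounded to 0.5%.
- If the wording means one subject in each of the three combination studies, 3/215 = 1.4%, which lies inside the range.

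**4. Six patients at the MTD.** P(at least 1) = 1 − (1−q)^6. P(at least 2) = 1 − (1−q)^6 − 6q(1−q)^5.

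| q | At least 1 of 6 | At least 2 of 6 |
|---|---|---|
| 0.5% | 3.0% | 0.04% |
| 2.3% | 13.0% | 0.7% |

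**5. Effect on escalation (illustration).** Suppose that other DLTs occur at an assumed 10% per patient, independently of anemia. Then p = 1 − 0.90(1−q), and the chance of two or more DLTs at a dose under 3+3 is 3p²(1−p) + p³ + 3p(1−p)²[1 − (1−p)³].

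- Anemia not counted (p = 0.100): 9.4%.
- Counted at q = 0.5% (p = 0.1045): 10.1%.
- Counted at q = 2.3% (p = 0.1207): 13.0%.

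**The case against.** The other side has real force on frequency. Section 1.2.5.4 describes most anemia as nonserious and confounded by disease and earlier therapy, and Section 1.3.5.7 gives Grade 3 or 4 anemia of 3% for single-agent ibrutinib. Eligibility sets neutrophil and platelet minimums but none for hemoglobin, so patients may enter anemic, and a Grade 3 or transfusion-based criterion could count the lymphoma rather than the drugs. Anemia would also be seen. Hemoglobin is part of every hematology panel, toxicity counts are reported, and the DSMC reviews toxicities every 4 months. All of this stands as an argument against a broad anemia criterion. None of it makes a related life-threatening or fatal case a DLT, and visibility to a committee is not the rule that sets the MTD.

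Two stronger readings are tempting.

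- A reader might infer that anemia is the commonest Grade 3+ event in the cited venetoclax NHL data. That holds only for the monotherapy study. The combination study and the program summary do not support it, and this trial is a combination.
- A reader might apply Grade 3+ rates of 5% to 16% and conclude that at least one of six patients would be affected with probability 26% to 65%, and two or more with probability 3% to 25%. The 16% is an all-cycle Grade 3+ rate, not a cycle 1 rate of life-threatening events. The serious-event record in Section 1.2.4 does not support life-threatening anemia in several patients at one dose level.

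**Conclusion.** The gap is real on the text and small in expected frequency. A related life-threatening or fatal anemia, or another unnamed hematologic event of that severity, meets no DLT criterion directly. The delay item catches only prolonged cases, if it applies to hematologic toxicity at all. The chance of at least one such anemia among six MTD patients is about 3% to 13%, and of two or more below 1%.

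The range assumes that serious-event rates from other venetoclax regimens carry over. Two features pull in opposite directions: those rates cover all cycles and all serious anemia, which overstates a cycle 1 life-threatening rate, while the higher venetoclax exposure with ibrutinib could raise it. The documents give no cycle 1 or Grade 4 figure to settle this. A broader anemia criterion is a debatable clinical choice and is not needed to close the gap.

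**What to change.** - In Sections 5.1 and 12, add one identical item so that related life-threatening or fatal hematologic events not otherwise named count as DLTs. Tie it to the life-threatening definition in Section 13.1.2 rather than to a laboratory grade. Otherwise it could take in lymphocyte decreases, which Section 1.2.3 regards as pharmacologic and non-adverse.
- State whether the item on delays of more than 7 days covers hematologic toxicity, and place it accordingly.
- Reconcile Sections 5.1, 7.2.4.1, 8.1.1 and 12 on how anemia and red-cell transfusion count. Any grade, duration or transfusion threshold is for the clinical team to set.

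The cost is amendment wording. Hemoglobin is already collected (Appendix 1). The downside is a rare extra DLT and cohort expansion; in the illustration, the chance of two or more DLTs at a dose rises from 9.4% to between 10.1% and 13.0%.
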